## PRÉCIS

Prevention of oral chronic graft versus host disease (GVHD) by topical agents is an attractive strategy because it would potentially avoid the adverse effects associated with systemic immunosuppression. Topically administered dexamethasone solution is a commonly used agent for the prophylaxis of oral inflammatory conditions including GVHD. However, the efficacy and systemic effects of topically administered dexamethasone solution are unknown. We therefore propose this trial designed to evaluate the efficacy and safety of topical dexamethasone solution for prevention of oral chronic GVHD in stem cell transplant recipients.

This pilot phase II study will follow a randomized, double-blind, placebo controlled, parallel group design. Consenting subjects who have undergone hematopoietic stem cell transplantation at the NIH Clinical Center and the surrounding transplant clinics will be randomized 50/50 to receive dexamethasone 0.01% solution or placebo as an oral rinse for 3 months starting 90-100 days post-transplant. Subjects will be evaluated monthly after the start of intervention. Diagnostic and research evaluations will include a complete oral examination, oral mucosal biopsy prior to the beginning of the intervention (day -7) and at the time of development of oral chronic GVHD or at the completion of intervention in the absence of clinical GVHD. We will measure serum dexamethasone levels and perform short cosyntropin (ACTH stimulation) test at the end of the 3 months of intervention or onset of clinically significant GVHD.

The primary objective of the study is to evaluate the safety and efficacy of topical dexamethasone 0.01% solution used as an oral rinse for prevention of oral chronic GVHD. Our primary endpoint will be the proportion of subjects that develop clinically significant (severity score 3 or higher) oral chronic GVHD after three months.

Secondary objectives will include the impact of oral chronic GVHD on the quality of life, characterization of the changes in tissue and salivary biomarkers associated with development of oral graft versus host disease, and measures of the effects of topical dexamethasone on hypothalamo-pituitary-adrenal axis. Secondary outcomes will include oral cavity specific quality of life as measured by OHIP-14 questionnaire, oral discomfort levels, improvement in general quality of life scores, and severity of oral chronic GVHD as measured by the site-specific GVHD scoring system.

---

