### **5.4.2 *Adrenal suppression***

Asymptomatic subjects without clinical signs of adrenal insufficiency and abnormal ACTH and/or cortisol test results at the end of the intervention period may be observed without steroid replacement and retested in 1 month. In case of development of symptoms suggestive of adrenal suppression (such as abdominal pain, nausea and vomiting, fatigue and hypotension) subjects will then be placed on the standard maintenance replacement regimen of the corticosteroids such prednisone 5-7.5 mg once daily and reevaluated in 1 month

by ACTH testing. All subjects with the abnormal ACTH test results will be advised of the symptoms and signs of clinically significant adrenal suppression and will be given stress doses of hydrocortisone injections for emergencies and a wrist bracelet.

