#### 8.4.6 Assessment of adrenocortical function (cortisol levels)

Subjects will be evaluated for possible hypothalamic-pituitary axis (HPA) axis suppression with the following measures:

1. Morning cortisol levels will be determined at baseline, monthly follow-ups (done at NIH), and at completion of the interventional phase (3 months after the last dose of study medication). The results will be blinded to the investigators until the end of the study. At the end of the study, in subjects with morning cortisol levels between 19 mcg/dL and 3 mcg/dL no further adrenal function testing will be performed.
2. In subjects with the symptoms of suspected adrenal insufficiency, a Short Cosynthropicin Test (SCT) will be performed to determine if the subject has HPA axis suppression. In brief: venous blood will be collected before administration of 250 mcg of cosyntropicin (synthetic ACTH) around 8 AM to 12 noon, and at 30 and 60 minutes after. The expected rise in cortisol levels is to at least 18 mcg/dL (24). In cases of minimally abnormal SCT (stimulated cortisol values of 13-17 mcg/dL), the test will be repeated the next day, as it has been demonstrated that the result is often normal with a repeat test. This test has been shown to be sensitive and specific for evaluation of subclinical adrenal suppression [52, 53]. In the unlikely event of significant adrenal suppression as assessed by repeat ACTH stimulation test, Clinical Center Endocrinology Service will be consulted. Pharmacy will be requested to unblind therapy to the endocrinologist so that appropriate therapy can be initiated and the endocrinologist can appropriately attribute the relationship of the event to study drug administration.
3. The confounding effect of systemic corticosteroids will be taken into account at the time of analysis. We expect to have a subgroup of subjects who will not receive systemic steroids. This subgroup will be used to evaluate the effects of topical dexamethasone on adrenal secretion.

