### **10.3 Risks and Discomforts**

#### **10.3.1 Related to dexamethasone**

The side-effects of topical steroids are usually limited to Candida (yeast) infection. This is relatively uncommon in our subject population (<5%), easily treatable and does not require discontinuation of the prophylaxis.

Low levels of topical steroids are absorbed through the oral mucosa, but the exact rate is not known. Possible risks associated with absorbed drug include:

- Adrenal suppression: While adrenal suppression is very rare with topically applied corticosteroids, it is physiologically possible. Cases of adrenal suppression following topically-applied steroid creams have been reported with long-term use on extensive body surface primarily in young children. In other reports, it was difficult to determine if there was true adrenal suppression. Symptoms of adrenal suppression are non-specific and include fatigue, nausea and abdominal discomfort. Since these symptoms are extremely common in the general hospital population, routine monitoring in the context of this study is not indicated. In this study, blood pressure will be monitored at every visit, and adrenal function will be assessed at the end of prophylaxis. Given the very short duration of this study, we do not expect significant side effects.

In the unlikely event of significant adrenal suppression as assessed by repeat ACTH stimulation test, Clinical Center Endocrinology Service will be consulted (see section 8.4.6, Assessment of Adrenocortical Function [Cortisol] levels).

- Growth and bone health: Impairment of childhood growth with an approximate cortisone dose of 1.5 mg/kg/day was first described over 40 years ago; osteopenia in children receiving a prednisolone dose of less than 0.16 mg/kg/day has also been reported. Loss of bone and deterioration in short term growth are dependent on the type and dose of glucocorticoid and occur most prominently over the first six months of treatment.

We will monitor pre-pubertal pediatric subjects by use of growth chart (length for age, weight for age percentiles and body mass index for age percentiles) and bone age (hand x-ray) if the results are available on the parent transplant protocol.

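### Section 8.4.6 ends adrenal testing for morning cortisol of 3 to 19 mcg/dL, gives no action outside that band, and disagrees with other sections on who is tested and when

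*Combined protocol and SAP*

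**What the plan says.** Section 8.4.6 sets out the adrenal assessment.

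- **Item 1** schedules morning cortisol and gives a rule for the study's end: "in subjects with morning cortisol levels between 19 mcg/dL and 3 mcg/dL no further adrenal function testing will be performed". Nothing is said about values below 3 or above 19 mcg/dL. Results are withheld from investigators until the end of the study.
- **Item 2** gives a symptom-based route to stimulation: "In subjects with the symptoms of suspected adrenal insufficiency, a Short Cosynthropicin Test (SCT) will be performed". The criterion for the stimulated value is "The expected rise in cortisol levels is to at least 18 mcg/dL". A next-day repeat is specified for "stimulated cortisol values of 13-17 mcg/dL". The endocrinology consult, and unblinding to the endocrinologist, follow significant suppression on a repeat test.

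Other sections cover the same ground:

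- The **Précis** says the study will "perform short cosyntropin (ACTH stimulation) test at the end of the 3 months of intervention or onset of clinically significant GVHD", with no cortisol or symptom condition.
- **Section 6.3** (month 3) lists serum cortisol, and lists the ACTH stimulation test as optional.
- **Section 6.5** (end of study) lists neither cortisol nor an ACTH test.
- **Section 5.4.2** says that asymptomatic subjects with "abnormal ACTH and/or cortisol test results at the end of the intervention period may be observed without steroid replacement and retested in 1 month".
- **Section 10.3.1** describes the symptoms of adrenal suppression as non-specific and continues: "Since these symptoms are extremely common in the general hospital population, routine monitoring in the context of this study is not indicated". It also commits to assessing adrenal function when prophylaxis ends.

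**The concern.** A rule that ends testing would be expected to apply where the result already in hand settles the question. Item 1 instead ends testing across a range that is mostly below the level item 2 looks for even after stimulation, and leaves unmentioned the high values that already exceed that level. The very low values are not mentioned either.

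The effect on adrenal cortical function is part of secondary objective 1.2.3. Section 2.5 says that systemic effects of the topical rinse have not been investigated and that some adrenal suppression is likely if absorption is significant. Item 2 itself recommends the stimulation test as a measure of subclinical suppression, which a symptom trigger would miss. If staff apply item 1 as written, a subject with low cortisol and no symptoms can leave the study with adrenal reserve unmeasured. If they apply the Précis, every subject is stimulated. The documents do not say which.

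**Working it through.** No sample size or power figure is involved. The check compares the protocol's own thresholds and then sets its sections side by side.

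**1. The band against the stimulated criterion**

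Inputs, all from 8.4.6: band 3 to 19 mcg/dL (unstimulated, morning); criterion at least 18 mcg/dL (stimulated); repeat range 13 to 17 mcg/dL (stimulated).

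- Width of the band: 19 − 3 = 16 mcg/dL.
- Part below 18: 18 − 3 = 15 mcg/dL, and 15/16 = 94% of the width.
- Part at or above 18: 19 − 18 = 1 mcg/dL, and 1/16 = 6% of the width.
- The numerical range 13 to 17, which item 2 treats as minimally abnormal after stimulation, lies wholly inside the band.

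These are shares of the band's width, not of subjects.

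| Morning cortisol (mcg/dL) | Item 1 | Relation to 18 before stimulation |
|---|---|---|
| 2 | no action stated | below |
| 4 | testing ends | below |
| 18.5 | testing ends | at or above |
| 20 | no action stated, not exempt | above |

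A morning value below 18 does not show that the stimulated value would fail. It only leaves the matter open, and that is where item 1 stops. At 20 the level is already reached, yet the exemption does not apply.

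**2. Who has the stimulation test**

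| Section | Rule |
|---|---|
| Précis | at the end of the 3 months or at GVHD onset, no condition |
| 6.3 | optional at month 3, no condition |
| 8.4.6 item 2 | subjects with symptoms |
| 8.4.6 item 1 | no further testing for 3 to 19 mcg/dL, at the end of the study |

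The first three cannot all be the rule. The third relies on symptoms that 10.3.1 regards as too common to be useful for monitoring.

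**3. When**

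Count months from the first dose, with a 3-month intervention.

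- 6.3 draws cortisol at month 3.
- 8.4.6 item 1 describes completion of the interventional phase as 3 months after the last dose: 3 + 3 = month 6.
- The end of the study is 6 months after initiation in the heading of 6.5, but 6 months after completing the intervention in 8.5: 3 + 6 = month 9.
- Item 1 applies at the end of the study, where 6.5 lists no cortisol or ACTH test.

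So the rule is tied to a visit with no scheduled adrenal measurement, and the visit with one (month 3) is not the time the rule names.

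**4. Route to the consult**

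The consult is described after a repeat test. A repeat is specified only for stimulated values of 13 to 17 mcg/dL. For values below 13, the documents do not state whether the test is repeated or how the subject reaches the consult.

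**The case against.** The strongest reply is that the two thresholds measure different things: the band is unstimulated morning cortisol, and 18 mcg/dL applies after 250 mcg of cosyntropin. That stands. A reader might infer that everyone in the band has failed the protocol's standard. The documents make 18 a criterion only for stimulated values, and morning values from 18 to 19 reach it anyway.

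Other stronger readings also go too far:

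- *That testing ends for every subject in the band.* Item 2 tests symptomatic subjects with no cortisol limit, and 6.3 offers the month-3 test without reference to the band. Those at risk of being missed are asymptomatic subjects who do not have the optional test.
- *That subjects are unmeasured when they stop the rinse.* Section 6.3 schedules serum cortisol then for all.
- *That item 1 flatly contradicts 5.4.2.* Section 5.4.2 concerns abnormal results, and no abnormal morning cortisol is defined. If 3 to 19 is not abnormal, the two can coexist. What is shown is a missing definition.
- *That a stimulated value below 13 has no pathway at all.* Section 5.4.2 provides for advice, emergency provisions and retesting after an abnormal ACTH test. Only the route to the consult is unstated.
- *That an incidence of suppression is invalidated.* The plan promises none. The scheduled baseline and month-3 cortisol values do not depend on the band, and item 3 plans to assess adrenal effects in subjects without systemic steroids.

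It is also fair to say that 10.3.1 regards adrenal suppression with topical steroids as very rare. That bears on how many subjects may be affected, not on whether the rule can be followed.

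**Conclusion.** The point holds as a defect in a stated safety rule. Followed literally, item 1 ends testing where the protocol's own figures leave adrenal status open and does not exempt values that already exceed 18 mcg/dL, so the sentence appears inverted. A reader might conclude that inversion is established. It is not: the text gives no rationale for the band, and only the sponsor can say what was meant.

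Independently of that sentence, three sections give three rules for who has the stimulation test, the timing in 8.4.6 does not match 6.3 or 6.5, and the path to the consult is incomplete.

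The size can be stated only in terms of thresholds: 15 of the 16 mcg/dL exempted lie below 18. The documents give no cortisol distribution and no expected uptake of the optional test, so the number of subjects who could be missed is unknown. The conclusion assumes the literal reading of item 1. The primary efficacy endpoint is unaffected, but the text needs correction because it governs participant safety monitoring.

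**What to change.** The sponsor, with the endocrinology service already named in 8.4.6, should:

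1. Confirm whether the end to testing in item 1 was meant for values inside or outside the 3 to 19 mcg/dL band, replace the sentence accordingly, and state what happens in every range.
2. State one rule for who has the stimulation test, and use it in the Précis, 6.3, 8.4.6 and 10.3.1.
3. Align the timing: when cortisol is drawn, which visit the rule refers to, and whether 6.5 should list an adrenal measurement.
4. Define what counts as an abnormal morning cortisol for 5.4.2, so that its retest provision can be read together with item 1.
5. State how each abnormal stimulated result, including values below 13 mcg/dL, relates to the repeat test and the consult.

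No threshold, test criterion or management rule is proposed here; those are for the sponsor and the endocrinology service. The cost is protocol wording, and possibly some stimulation tests that the Précis and 6.3 already foresee.

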### 8.5 Data Analyses

This study will be analyzed according to the “intent to treat” principle, that is, all randomized subjects will be included. Subjects not evaluated for endpoints will be considered to have reached the primary endpoint. Every effort will be made to reach and evaluate the subjects at the monthly intervals and at the end of the 3 month intervention period. The differences in proportions of significant oral chronic GVHD will be assessed by a chi-squared test (with continuity correction). Treatment group differences in the severity scores, pain and xerostomia scores, and quality of life scores (OHIP-14) will be assessed using the Wilcoxon test. Adjustments will be made for age and other covariates of interest, such as systemic immunosuppression. Adverse events will be tabulated by severity and treatment assignment. For pediatric subjects, analyses will include growth assessment (growth chart [length for age, weight for age percentiles

and body mass index] for age percentiles) and bone age and the associated z-scores (the number of standard deviations the child's measures [weight, height etc] differ from the population mean).

The intervention period will be 3 months. Should the subject reach the primary endpoint (development of clinically significant oral chronic GVHD), the subject will be asked to participate in end of study assessments and then will go off study. Subjects who did not develop oral chronic GVHD in the intervention phase of the study will be followed for up to 6 months to document late development of oral chronic GVHD. All subjects will be evaluated after 6 months after completion of the intervention phase of the study in the absence of clinical oral GVHD. Final statistical analysis will be performed once all subjects in the sample have completed the study and all records have been collected. We will use stratified analyses to account for effects of systemic immunosuppressive agents and other prognostic factors.

In the event of a protocol violation, the aggregate data will be analyzed with and without those subjects involved in the incident.

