### 9.2 Adverse Events

Because dexamethasone is an FDA approved drug with known toxicity profile, any observed or volunteered adverse events will not be captured in the database unless (1) the adverse event is previously unknown (not on the label) or more severe than on the label and deemed possibly, probably or definitely related to the study medication or (2) meets the criteria for a severe adverse event. Adverse events that are complications of the primary transplant protocol and deemed unlikely or unrelated to dexamethasone will not be captured in the database for this protocol, but will be collected and reported in the transplant protocol. The collection of AE information will begin on the first day of initiation of the study drug.

The NCI Common Terminology Criteria for Adverse Events Version 4 (CTCAE) will be used for toxicity and adverse event reporting. All appropriate treatment areas have access to a copy of the CTCAE version 4.0. A copy of the CTCAE version 4.0 can be downloaded from the CTEP web site (<http://ctep.cancer.gov>).

**Adverse event** is defined according to 21 (CFR 312.32(a)) as any untoward medical occurrence associated with the use of a drug in humans, whether or not considered drug related. An adverse event can also be any unfavorable and unintended diagnosis, symptom, sign (including an abnormal laboratory finding), syndrome, or disease temporally associated with the use of a drug, without any judgment about causality. Adverse event either occurs during the study participation, having been absent at baseline or if present at baseline, appears to worsen.

An abnormal laboratory value will be considered an AE if the laboratory abnormality is characterized by any of the following:

- Results in discontinuation from the study
- Is associated with clinical signs or symptoms
- Requires treatment or any other therapeutic intervention
- Is associated with death or another serious adverse event, including hospitalization
- Is judged by the Investigator to be of significant clinical impact
- If any abnormal laboratory result is considered clinically significant, the investigator will provide details about the action taken with respect to the test drug and about the patient's outcome.

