### **9.3 Serious Adverse Events**

A serious adverse event is any untoward medical occurrence that:

- results in death
- is life-threatening, requires or prolongs hospitalization
- causes persistent or significant disability/incapacity
- results in congenital anomalies/birth defects
- or in the opinion of the investigators represents other significant hazards or potentially serious harm to research subjects or others.

Only those SAEs that are determined possibly, probably or definitely related to this protocol will be reported on this ancillary study. Those determined possibly, probably or definitely to post transplant complications will be reported on the transplant protocol.

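### Section 8.4.6 has adrenal suppression attributed with the arm known while 9.2 to 9.4 filter events by relatedness, which can tilt the by-arm safety counts against dexamethasone

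*Combined protocol and SAP*

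**What the plan says.** Section 8.4.6 sets the trigger: "In the unlikely event of significant adrenal suppression as assessed by repeat ACTH stimulation test, Clinical Center Endocrinology Service will be consulted". It then breaks the code for one person: "Pharmacy will be requested to unblind therapy to the endocrinologist so that appropriate therapy can be initiated". The same sentence adds a second purpose, that "the endocrinologist can appropriately attribute the relationship of the event to study drug administration". Section 4.3 otherwise keeps investigators and subjects blinded until the study is complete.

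Section 9.2 opens two routes into the adverse event database. An event enters if "the adverse event is previously unknown (not on the label) or more severe than on the label" and it is "deemed possibly, probably or definitely related to the study medication or (2) meets the criteria for a severe adverse event". The next sentence takes some events out again: of complications of the transplant protocol, those "deemed unlikely or unrelated to dexamethasone will not be captured in the database for this protocol", and they are reported under the transplant protocol instead.

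For serious events, section 9.3 says: "Only those SAEs that are determined possibly, probably or definitely related to this protocol will be reported on this ancillary study". Section 9.4 puts before the DSMB the serious events considered at least possibly related to the study agent, and sends those due to post-transplant complications to the transplant protocol.

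Section 8.5 uses the data comparatively: "Adverse events will be tabulated by severity and treatment assignment". Safety is part of the primary objective (section 1.1), and adrenal suppression is the first risk of absorbed drug listed in section 10.3.1.

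**The concern.** Filtering safety events by relatedness does limited harm to a between-arm comparison when the judgement is blind: events with the same clinical picture are kept or dropped alike in both arms. It becomes a problem when the person judging knows the arm. An adrenal event in a subject known to be on placebo can hardly be called related to dexamethasone, and systemic steroids, which section 5.2.2 permits, offer a ready transplant-side explanation. The same event in a subject known to be on the active rinse can reasonably stay at possibly related.

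At stake is the comparison of adrenal adverse events in a trial whose primary objective includes safety. The error has a known direction: it makes dexamethasone look worse than it is. The events affected are the confirmed significant cases, which matter most for safety.

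**Working it through.** The plan states no figure for adrenal events, so the main check sets the rules side by side. A small calculation then gives a sense of scale.

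**Step 1. Which events are attributed with the arm known?** Only significant suppression on a repeat stimulation test (8.4.6). Other adrenal findings stay with blinded staff.

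**Step 2. What happens to such an event under each rule?**

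| Class of event | Rule | Judged related | Judged unrelated and a transplant complication |
|---|---|---|---|
| Not severe, on the label and no worse than labelled | 9.2, first route fails | Not captured | Not captured |
| Not severe, unlabelled or worse than labelled | 9.2, first route | Captured | Not captured |
| Severe | 9.2, second route (no relatedness condition) against the exclusion sentence | Captured | Unclear: 9.2 does not say which sentence prevails |
| Serious | 9.3 and 9.4 | Reported here and reviewed by the DSMB | Transplant protocol only |

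The first row gives no difference between arms. Whether adrenal suppression is on the label is an assumption, since the label is not in the documents; section 10.3.1 treats it as an anticipated risk. The serious row makes reporting depend on attribution outright. The severe row does so if the exclusion sentence prevails.

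**Step 3. Who decides relatedness?** Sections 9.2 to 9.4 do not say. The only procedure the plan describes for attributing confirmed adrenal suppression is the unblinded one in 8.4.6. No section asks for a blinded judgement beforehand.

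**Step 4. Scale.** Inputs: 36 per arm (section 8.2); a true rate q of severe or serious confirmed adrenal events, the same in both arms, so no effect of the rinse; a retained fraction r in each arm. Both q and r are assumptions.

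- Expected recorded count per arm = 36 × q × r. For q = 0.05 and r = 1 this is 36 × 0.05 = 1.8.
- The chance that dexamethasone shows more recorded events than placebo is the sum over a > b of the two binomial probabilities with n = 36 and success probability q × r in each arm. When nothing is kept on placebo and everything on dexamethasone, it reduces to 1 − (1 − q)^36. For q = 0.05: 1 − 0.95^36 = 0.842.

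| q | All kept in both arms | All on dexamethasone, half on placebo | All on dexamethasone, none on placebo | Half on dexamethasone, none on placebo |
|---|---|---|---|---|
| 3% | 1.08 v 1.08; 35% | 1.08 v 0.54; 49% | 1.08 v 0; 67% | 0.54 v 0; 42% |
| 5% | 1.8 v 1.8; 39% | 1.8 v 0.9; 59% | 1.8 v 0; 84% | 0.9 v 0; 60% |
| 10% | 3.6 v 3.6; 42% | 3.6 v 1.8; 72% | 3.6 v 0; 98% | 1.8 v 0; 84% |

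Each cell gives expected recorded counts, dexamethasone v placebo, then the chance of more recorded events on dexamethasone. Equal capture gives less than 50% because ties are possible.

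**The case against.** The strongest reply is that the rules do not combine as neatly as this suggests.

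- The first route in 9.2 needs an unlabelled or worse-than-labelled event as well as relatedness, so a non-severe case may drop out of both arms. This stands.
- The second route in 9.2 has no relatedness condition, so a severe placebo case is lost only if the exclusion sentence overrides it. This stands as an ambiguity; it does not clear the text.
- Sections 9.3 and 9.4 concern serious events only, and an abnormal stimulation test is not serious in itself. Non-serious adrenal suppression reaches the DSMB from neither arm. This stands.
- Nothing says the endocrinologist's opinion governs capture, and investigators remain blinded. True, but no one else is named for this judgement, so the gap needs closing.
- Excluded events go to the transplant protocol and are not destroyed. True, but they are missing from this trial's by-arm table.
- Cortisol is measured in both arms with results blinded, 8.4.6 reserves a subgroup without systemic steroids, and 8.5 plans stratified analyses for systemic immunosuppression. These protect the laboratory question. They do not repair the adverse event table or the DSMB's information.

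A reader might infer more: that every adrenal event is recorded on dexamethasone and discarded on placebo, so that the table is biased by construction. The first three replies and the routing to the transplant protocol rule that out. A reader might also attach significance tests, for example 5, 6 or 7 cases of 36 against 0 of 36 (two-sided Fisher p = 0.054, 0.025 and 0.011). The arithmetic is right, but it assumes 14% to 19% of subjects affected in each arm and complete differential capture. The plan calls such suppression unlikely, makes the stimulation test optional at 3 months (6.3) and plans to tabulate adverse events, with no test of them described.

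**Conclusion.** The concern holds in a limited form. Attribution with the arm known, combined with relatedness-dependent capture and no rule on whose judgement governs, can bias this trial's by-arm count of severe or serious adrenal events against dexamethasone. It need not do so.

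The size cannot be determined from the documents. On assumed equal true rates of 3% to 10% with 36 per arm, the worst case is an expected 1.1 to 3.6 recorded events versus 0. Dexamethasone would then show the higher count 67% to 98% of the time, against 35% to 42% with equal capture. Keeping half the placebo events brings this to 49% to 72%. These figures rest on the assumed rates, on every such case being unblinded, and on the unblinded attribution governing capture. The efficacy endpoint and the cortisol comparison are unaffected. This is a cheap improvement to the safety comparison; it does not undermine the trial.

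**What to change.** Make three changes, all to data recording:

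1. In 8.4.6, keep the unblinding of the endocrinologist for care exactly as written, but delete attribution as one of its purposes.
2. Have the blinded investigator record causality before the code is broken, and state that this attribution governs 9.2, 9.3 and reporting to the DSMB under 9.4.
3. In 9.2, record every confirmed abnormal stimulation test in this study's database, in both arms, whatever the attribution. This also settles, for these events, the conflict between the two sentences in 9.2 and the loss of non-severe labelled cases.

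The cost is a few sentences in 8.4.6 and 9.2 and one dated causality entry per case. The downside is that a few background events caused by systemic steroids enter the table. They would be recorded by the same rule in both arms, so they add noise without favouring either.
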